4.4.2.1.2. Study Insulin Dose Analysis

For study insulin dose, the average daily dose in U, weekly dose in U and daily dose in U/kg during each visit for individual participants will be used in the analysis.

In the LY3209590 group,

- the average dose of each visit (that is, average of weekly doses since last visit) will be used as the average weekly dose in U;
- the average daily dose in U will be the average weekly dose in U divided by 7;
- the average daily dose in U/kg will be the average daily dose in U divided by body weight for the visit.

In the insulin degludec group,

- the average dose of each day within a visit (that is, average of each day doses since last visit) will be used as the average daily dose in U;
- the average weekly dose in U will be calculated by the average daily dose in U multiplied by 7;
- the average daily dose in U/kg will be the average daily dose in U divided by last measured body weight on or prior to the visit.

For participants using typical once-daily pre-study basal insulin, the average pre-study basal dose during the lead-in period will be the baseline daily dose in U. For participants using pre-study U-300 or NPH BID, the average pre-study basal dose during the lead-in period multiplied by 0.8 will be the baseline daily dose in U. The baseline daily dose in U multiplied by 7 will be the baseline weekly dose in U for the study insulin dose analysis. The baseline daily dose in U divided by baseline weight will be the baseline daily dose in U/kg.

4.4.2.1.3. Analysis of Fasting Blood Glucose

The analysis of fasting blood glucose (FBG), measured by SMBG, will be analyzed (in both CN and SI units). If a subject does not indicate which BG measurement was fasting, the FBG value will be assigned programmatically by designating the FBG as the first measurement between 5am-10am. These programmatically derived FBG values will also be included in the analysis.

4.4.2.2. **Other Safety Endpoints**

The safety measures based on CGM data will be analyzed as described in Section 4.4.2.1.1. For other safety measures, the details are provided in Section 4.6.

4.4.2.3. **Patient Reported Outcome**

The analyses for patient-reported outcomes will be based on the EAS2 data.

4.4.2.3.1. Treatment-Related Impact Measure – Diabetes (TRIM-D)

The TRIM-D is a self-administered instrument, which assesses the impact of diabetes treatment on participants' functioning and well-being across available diabetes treatments (Brod et al. 2009). The TRIM-D consists of 28 items each assessed on a 5-point scale, where higher scores indicate a better health state, with a recall period of "over the past 2 weeks." In addition to an overall score, the TRIM-D items assess 5 domains of impact:

- Treatment Burden (6 items: Question 1a, Question 2a to 2e),
- Daily Life (5 items: Question 3a to 3b, Question 5a to 5c),
- Diabetes Management (5 items: Question 4a to 4e),
- Compliance (4 items: Question 6a, b, c, e), and
- Psychological Health (8 items: Question 6d, Question 7a to 7g).

Items within each domain are summed to obtain a raw domain score, which is then transformed to a scale of 0 to 100 to obtain a transformed domain score. The transformed domain score can be calculated by:

 $\frac{(\text{sum of raw score - sum of lowest possible raw score)}}{(\text{sum of highest possible raw score - sum of lowest possible raw score)}} \times 100$

For an example, Diabetes Management = $([sum of raw score -5]/[25-5]) \times 100$. If answer for the 5 questions in Diabetes Management (Question 4a to 4e) are all 1, then the sum of raw score is 5 and the transformed domain score is 0. All items can also be summed and transformed to obtain a transformed total score in a similar way.

Summary statistics for the transformed scores of each domain and all domains will be provided by study treatment. The scores at scheduled visits and the change from baseline will be analyzed by the MMRM model similar to the other efficacy endpoints (see Section 4.4.2.1). The last

non-missing postbaseline observations will be analyzed by an ANCOVA model using the independent variables of treatment, strata (country, and the type of basal insulin at randomization, baseline HbA1c stratum), and baseline value of the dependent variable as independent variables.

4.4.2.3.2. Diabetes Treatment Satisfaction Questionnaire (DTSQ)

Diabetes Treatment Satisfaction Questionnaire-Status (DTSQs)

The Diabetes Treatment Satisfaction Questionnaire-Status Version (DTSQs) (Bradley and Lewis 1990; Bradley 1994) is a diabetes-specific patient-reported outcome instrument that assesses the overall treatment satisfaction and perceived frequency of hyperglycemia and hypoglycemia. It is appropriate for use in both T1D and T2D. The DTSQs consists of 8 items that assess treatment satisfaction as well as concerns about hyperglycemia and hypoglycemia over the past few weeks, prior to the visit. Each item is rated on a 7-point Likert scale. Items 1 and 4-8 are rated from 0 (very dissatisfied) to 6 (very satisfied) and can be summed up to produce a treatment satisfaction score ranging from 0 to 36. Items 2 and 3 are scored individually, and evaluate the perceived frequency of hyperglycemia and hypoglycemia and are rated from 0 (none of the time) to 6 (most of the time).

The collection of DTSQs is planned prior to the initiation of study treatment. The total scores of Item 1 and 4-8 and the individual scores of Items 2 and 3 will be summarized. Wilcoxon rank-sum test will be used for treatment comparison.

Diabetes Treatment Satisfaction Questionnaire-Change (DTSQc)

The Diabetes Treatment Satisfaction Questionnaire-Change Version (DTSQc) (Bradley 1999) was designed to overcome potential ceiling effects in the status version. The DTSQc has the same 8 items as the status version but is reworded slightly to measure the change in treatment satisfaction rather than absolute treatment satisfaction. Each item is scored on a scale of -3 to +3. For all items except item 2 (perceived frequency of hyperglycemia) and item 3 (perceived frequency of hypoglycemia), the higher the score, the greater the improvement in treatment satisfaction and a score of 0 represents no change. For Items 2 and 3, the lower the score, the better the perception. The ratings for Items 1 and 4-8 are summed to obtain a total treatment satisfaction score ranging from -18 to 18. Items 2 and 3 are scored individually.

The collection of DTSQc is planned after the initiation of study treatment. The total scores of Item 1 and 4-8 and the individual scores of Items 2 and 3 will be summarized. Wilcoxon rank-sum test will be used for treatment comparison.

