# 3. Objectives, Endpoints, and Estimands

Objectives	Endpoints
Primary	
• To investigate the hypothesis that LY3209590 is noninferior to the comparator (insulin degludec) on glycemic control in study participants with T2D currently on basal insulin	• Change from baseline in HbA1c at Week 26
Key Secondary (Multiplicity Adjusted)	
• To demonstrate LY3209590 is superior to insulin degludec in the selected parameters of glycemic control	
 
Change from baseline in HbA1c at Week 26
 
The event rate of participant-reported clinically significant nocturnal hypoglycemia (<54 mg/dL [3.0 mmol/L] or severe) during treatment phase up to Week 78
 
Time in glucose range between 70 and 180 mg/dL (3.9 and 10.0 mmol/L) inclusive measured during the CGM session prior to Week 26
 

Other Secondary	
• To investigate the efficacy of LY3209590 compared with insulin degludec in additional parameters of glycemic control	
 
Change from baseline in HbA1c at Weeks 52 and 78
 
Change from baseline in fasting glucose measured by SMBG at Weeks 26, 52, and 78
 
Glucose variability measured during the CGM session prior to Weeks 26, 52, and 78
 
Time in glucose range between 70 and 180 mg/dL (3.9 and 10.0 mmol/L) inclusive measured during the CGM session prior to Weeks 52 and 78
 
Insulin dose at Weeks 26, 52, and 78
 

• To investigate the safety of LY3209590 compared with insulin degludec	
 
Incidence and rate of composite of Level 2 and 3 hypoglycemia events during treatment period
 
Body weight change from baseline to Weeks 26, 52, and 78
 
Time in hypoglycemia with glucose <54 mg/dL (3.0 mmol/L) measured during the CGM session prior to Weeks 26, 52, and 78
 
Time in hyperglycemia range defined as glucose >180 mg/dL (10.0 mmol/L) measured during the CGM session prior to Weeks 26, 52, and 78
 

• To evaluate treatment impact between LY3209590 and insulin degludec based on patient-reported outcomes questionnaires	
 
Change from baseline in TRIM-D at Weeks 26, 52, and 78
 
DTSQ change from baseline at Weeks 26, 52, and 78
 

Tertiary	

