## 8.1.5.6. Patient-Reported Outcomes Assessments

The self-administered questionnaires will be translated into the native language of the region and administered at the site during the designated visits in the SoA (Section 1.3) At these visits, the questionnaires should be completed before the participant has discussed their medical condition

or progress in the study with the investigator and/or site staff, if the participant is not adversely affected by their fasting condition.

Preferred administration order of these questionnaires throughout the trial are

- 1. TRIM-D
- 2. DTSQ (status) (baseline only)
- 3. DTSQ (change) (after randomization)
- 4. EQ-5D-5L
- 5. SIM-Q
- 6. Basal Insulin Experience: Preference, and
- 7. Basal Insulin Experience: Likelihood of incorporating into routine.

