4.1. General Considerations

Statistical analysis of this study will be the responsibility of Eli Lilly and Company (Lilly) or its designees. Any change to the data analysis methods described in the protocol will require an amendment ONLY if it changes a principal feature of the protocol. Any other changes to the data analysis methods described in the protocol, and the justification for making the change, will be described in this SAP or the clinical study report. Additional exploratory analyses of data will be conducted as deemed appropriate.

Unless otherwise stated, the efficacy analyses will be based on either efficacy analysis set 1 (EAS1, see the definition in Section 3) or efficacy analysis set 2 (EAS2, see the definition in Section 3). For treatment regimen estimand, EAS1 will be used. For efficacy estimand, other secondary and tertiary efficacy measures, EAS2 will be used (using the data up to the intercurrent events). The treatment comparison will be based on either 2-sided test or 95% CI.

Unless otherwise noted, the safety analyses will be conducted on the Safety Analysis set (SS, see the definition in Section 3). Percentages will be calculated using the mITT population as the denominator. For events that are sex-specific, the denominator and computation of the percentage will include only participants from the given sex.

For continuous measures, summary statistics will include sample size, mean, SD, median, minimum, and maximum for both the actual and the change from baseline measurements. For certain variables that are considered to be log-normally distributed, the geometric mean and coefficient of variation (CV) will be provided instead. Either the mixed model repeated measurement (MMRM) model or the analysis of covariance (ANCOVA) model will be used to analyze continuous outcomes. Least-squares (LS) means, and standard errors derived from the analysis models will also be displayed. Treatment comparisons will be displayed showing the treatment difference LS means and the 95% CIs for the treatment differences, along with the p-values for the treatment comparisons. For certain safety laboratory measures, log-transformed values will be analyzed in the statistical model instead. The actual, change from baseline and percentage change from baseline will be presented using the derivation based on the output from the statistical model and the assumption of lognormality.

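### The DTSQc total score is compared only by an unadjusted Wilcoxon test, with no estimate of the treatment difference, while baseline DTSQs and the randomization strata go unused

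*SAP*

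**What the plan says.** Protocol Section 3 lists "DTSQ change from baseline at Weeks 26, 52, and 78" among the other secondary endpoints, under the same objective as TRIM-D.

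SAP 4.4.2.3.2 treats the two versions of the questionnaire separately:

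- Status version: "The collection of DTSQs is planned prior to the initiation of study treatment". Protocol 8.1.5.6 likewise restricts it to baseline.
- Change version: "The collection of DTSQc is planned after the initiation of study treatment". Its main score is defined thus: "The ratings for Items 1 and 4-8 are summed to obtain a total treatment satisfaction score ranging from -18 to 18". The two perception questions (items 2 and 3) remain single-item scores, each running from -3 to +3.

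For each version the SAP promises summaries and then says "Wilcoxon rank-sum test will be used for treatment comparison". The sentence appears twice; this point concerns its second use, for DTSQc.

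For TRIM-D, SAP 4.4.2.3.1 says: "The scores at scheduled visits and the change from baseline will be analyzed by the MMRM model similar to the other efficacy endpoints". It adds an ANCOVA of the last available score with strata and baseline. SAP 4.5.3.1 gives EQ-5D-5L, a tertiary measure, the same treatment. The general rule in SAP 4.1 reads: "Either the mixed model repeated measurement (MMRM) model or the analysis of covariance (ANCOVA) model will be used to analyze continuous outcomes", with LS mean differences, 95% CIs and p-values displayed.

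**The concern.** A summed score with 37 possible values, at three visits, is compared by a method that returns a p-value and no treatment difference. A reader who wants to know how much satisfaction differs between weekly and daily insulin gets no model-based estimate or interval. That gap exists whatever the data look like.

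The second loss is precision. Baseline satisfaction is measured in everyone scheduled for Visit 3, and randomization is stratified by country, HbA1c and basal insulin type. None of this enters the DTSQc comparison. The baseline questionnaire is instead used to compare the arms before treatment, where any difference is due to chance under randomization.

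What is at stake is limited. DTSQc carries no share of alpha and no power statement, and no primary or key secondary conclusion depends on it.

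**Working it through.** **Passages side by side**

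| Measure | Tier | Baseline covariate | Strata | Estimate and CI |
|---|---|---|---|---|
| TRIM-D (SAP 4.4.2.3.1) | Other secondary | Yes | Yes | Yes, from MMRM and ANCOVA |
| EQ-5D-5L (SAP 4.5.3.1) | Tertiary | Yes | Yes | Yes, from MMRM and ANCOVA |
| DTSQc total (SAP 4.4.2.3.2) | Other secondary | No | No | None named |

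No other section of either document supplies an adjusted DTSQc analysis.

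**Inputs**

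- From SAP Section 5: 939 randomized 2:1, 15% dropout at Week 26, 532 and 266 completers.
- Assumed: the size r of the correlation between baseline DTSQs and DTSQc. The documents give no correlation, SD or effect size for DTSQ.

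**The plan's own figures**

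- Completers: 626 × 0.85 = 532.1 and 313 × 0.85 = 266.05, together about 798, as stated.
- Check on HbA1c superiority: √(1/532 + 1/266) = 0.0751, so SE = 1.1 × 0.0751 = 0.0826. Then 0.3/0.0826 = 3.63, and power = Φ(3.63 − 1.96) = 95.3%, against the stated 95%.

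**Gain from adjustment**

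Adjusting for one baseline covariate multiplies the variance of the treatment difference by 1 − r². The last column is Φ(2.80/√(1 − r²) − 1.96), where 2.80 = 1.96 + 0.84.

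| Assumed r | Variance removed, r² | Equivalent completers, 798/(1 − r²) | CI width ratio, √(1 − r²) | Power of adjusted rank analysis when Wilcoxon has 80% |
|---|---|---|---|---|
| 0 | 0% | 798 | 1.000 | 80.0% |
| 0.2 | 4% | 831 | 0.980 | 81.6% |
| 0.3 | 9% | 877 | 0.954 | 83.6% |
| 0.4 | 16% | 950 | 0.917 | 86.4% |
| 0.5 | 25% | 1,064 | 0.866 | 89.9% |

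The standardized difference detectable with 80% power is 2.80 × 0.0751 = 0.210 SD for an unadjusted linear model. For Wilcoxon under normality it is 0.210/√(3/π) = 0.215. For ANCOVA it is 0.210 × √(1 − r²), that is 0.201 at r = 0.3 and 0.182 at r = 0.5.

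**Direct comparison with Wilcoxon**

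The equivalent-completer column compares adjusted with unadjusted analyses of the same type. A simulation therefore compared the methods directly: 2,000 runs, 532 against 266, integer scores limited to -18 to 18, and an effect of 0.22 SD. The correlation and effect apply before rounding and truncation.

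| Score shape | r | Wilcoxon | ANCOVA | Rank ANCOVA |
|---|---|---|---|---|
| Near normal | 0 | 0.82 | 0.84 | 0.82 |
| Near normal | 0.3 | 0.82 | 0.87 | 0.84 |
| Near normal | 0.5 | 0.81 | 0.92 | 0.90 |
| Truncated at ceiling | 0 | 0.79 | 0.79 | 0.79 |
| Truncated at ceiling | 0.3 | 0.80 | 0.83 | 0.83 |
| Truncated at ceiling | 0.5 | 0.80 | 0.88 | 0.89 |

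With no effect, all three methods rejected in about 4% to 6% of runs. These calculations cover the baseline covariate only. Any further gain from the strata is not quantified.

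**The case against.** The best defence is that the Wilcoxon test is a sound choice for bounded sums of ordinal items. It is valid under randomization and robust to the score's shape. The SAP uses it for SIM-Q and the Basal Insulin Experience questions, and its version history gives suitability for ordinal data as the reason in the latter case. This stands for DTSQc items 2 and 3. It is weaker for the total, which is a summed Likert score like TRIM-D, for which the SAP accepts linear models.

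A second defence is that the reader is not left empty-handed. SAP 4.1 calls for means and SDs, from which a crude difference and interval can be derived. It allows comparisons by either a test or a 95% CI, and it lists both the scheduled visits and the last collection for patient-reported outcomes, so visit handling is not wholly open. All of that stands, but a derived crude difference is neither prespecified nor adjusted.

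Third, a reader might infer that DTSQs is collected in order to adjust DTSQc. Neither document says so; they give only its timing. A reader might also infer from the purpose of DTSQc that its scores must depend strongly on baseline. The SAP says that DTSQc was devised to get round ceiling effects in the status version. An instrument that succeeds in this could depend less on baseline, so the text supports no particular r.

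Finally, the TRIM-D model cannot be carried over unchanged. It adjusts for the outcome's own baseline value, and DTSQc has none. DTSQs is a different version, scored 0 to 36.

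**Conclusion.** The point holds as one of efficiency and reporting, with low materiality. The DTSQc total is the exception among the summed patient-reported scores: it has no adjusted analysis and no planned estimate with an interval, and the SAP gives no reason.

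The missing estimate does not depend on any assumption. The loss of precision does: it is nil at r = 0, 4% of the variance at r = 0.2, 9% at 0.3 and 25% at 0.5. A reader might quote the gain as worth 10% to 33% more participants (877/798 and 1,064/798). That range presupposes r between 0.3 and 0.5, which the documents do not support, and it is not a comparison with Wilcoxon itself. Against Wilcoxon, the simulated power gain at r = 0.3 was 2 to 5 percentage points. Only near r = 0.5 was it notable, at 8 to 11 points.

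Nor do the documents support reading this as bias or type I error inflation. The test is valid, and the endpoint lies outside the multiplicity-controlled family.

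**What to change.** Amend SAP 4.4.2.3.2 as follows:

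- Analyse the DTSQc total with an MMRM across Weeks 26, 52 and 78, and with an ANCOVA for the last observation, as for TRIM-D.
- Use the baseline DTSQs total in place of the outcome's own baseline, and include country, basal insulin type and HbA1c stratum.
- Report the LS mean difference with its 95% CI at each visit.
- Keep the Wilcoxon test of the total as a sensitivity analysis.
- Keep Wilcoxon for items 2 and 3, or use a rank analysis adjusted for the matching DTSQs item.

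The change needs no new data. It costs a paragraph of SAP text and one new covariate specification in a model family already planned. The drawback is that participants without a baseline DTSQs drop out of the adjusted model; the unadjusted Wilcoxon analysis would still include them.

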4.5. Tertiary Endpoint Analysis

4.5.1. Tertiary Efficacy Endpoints

4.5.1.1. Fasting Serum Glucose

Fasting serum glucose (FSG), measured by central laboratory, will be analyzed (for both international units [SI] and conventional units [CN]) for both treatment regimen estimand and efficacy estimand using same ANCOVA (at Weeks 26, 52 and 78) and MMRM model (at all scheduled visits), respectively as described in Section 4.3.2 with an additional term of baseline

HbA1c stratum (< 8.0%, $\geq 8.0\%$), using data from EAS1 and EAS2, respectively. Missing data imputation and analysis set will be the same as described in Section 4.4.2.1.

4.5.1.2. Binary outcomes for HbA1c target

For analysis of the binary outcomes, the details are provided in the table below:

Analysis Population	All participants in EAS1 with non-missing baseline measure		
Analysis	All non-missing observations at baseline and at the specified timepoints regardless of the use of		
Data	study intervention or rescue medications.		
Endpoint	1) HbA1c target (< 7% or \leq 6.5%) at the specified timepoints;		
	2) The composite of		
	a) binary outcome of HbA1c <7% at Week 26, and,		
	b) binary outcome of no nocturnal level 2 or 3 hypoglycemia during treatment phase up to		
	Week 26.		
	3) The composite of		
	a) binary outcome of HbA1c <7% at Week 26, and,		
	b) binary outcome of no level 2 or 3 hypoglycemia during treatment phase up to Week 26		
	with "Yes" indicating achieving the target (in respective endpoints defined above).		
Missing	1) For HbA1c, missing values at the specified timepoints will be imputed using the same		
Data	method for the primary endpoint (Section 4.3.2).		
	2) For hypoglycemia that are included in the composite endpoints, a participant who		
	discontinued both treatment and treatment period before Week 26 (Visit 22) is considered as		
	a non-responder (i.e. experienced the event).		
Analysis	These endpoints will be analyzed using a logistic regression model including		
Model	- independent variables of treatment,		
	- strata (country, and the type of basal insulin at randomization),		
	- baseline HbA1c value		
	- additionally, for the composite endpoint		
	 baseline incidence of hypoglycemia and, 		
	• interaction term of baseline HbA1c value * baseline incidence of		
	hypoglycemia; if the model fails to converge, the interaction term will be		
	removed.		
	The unconditional treatment group effect will be assessed based on a robust variance estimator		
	for g-computation estimators (Ye et al. 2023). The estimated treatment group-specific odds ratio,		
	p-value, and 95% CI will be used for treatment comparison. The statistical inference will be		
	based on the multiple imputation framework by Rubin (1987).		

Abbreviations: EAS1 = efficacy analysis set 1; HbA1c = hemoglobin A1c.

Note 1: Levels of hypoglycemia events and nocturnal events are defined in Section 4.6.3.1.1.

4.5.2. Tertiary Safety Endpoints

For tertiary safety measures, the details are provided in Section 4.6 and the following subsections.

4.5.3. Tertiary Patient Reported Outcomes

4.5.3.1. EQ-5D-5L

The EQ-5D-5L (EuroQol Research Foundation 2019) is a standardized 5-item self-administered instrument for use as a measure of health outcome. It provides a simple descriptive profile and a single index value for health status that can be used in the clinical and economic evaluation of health care as well as population health surveys. The EQ-5D-5L assesses 5 dimensions of health:

- mobility,
- selfcare,
- usual activities,
- pain/discomfort, and
- anxiety/depression.

The 5L version, scores each dimension at 5 levels:

- no problems,
- slight problems,
- moderate problems,
- severe problems, and
- unable to perform/extreme problems.

In addition to the health profile, a single health state index value can be derived based on a formula that attaches weights to each of the levels in each dimension. This index value ranges between less than 0 (where 0 is a health state equivalent to death; negative values are valued as worse than dead) to 1 (perfect health).

The second part of the questionnaire consists of EQ Visual Analog Scale (VAS) which records the respondent's self-rated health status. The participant rates his/her perceived health from 0 (the worst imaginable health) to 100 (the best imaginable health). In conjunction with the health state data, it provides a composite picture of the respondent's health status.

The frequency and proportion of each level for a given item will be summarized by study treatment for each scheduled visit. The EQ-5D-5L index, EQ VAS score and their change from baseline will be analyzed by the MMRM model similar to the other efficacy endpoints (see Section 4.4.2.1) for the scheduled postbaseline visits and by the ANCOVA model similar to the TRIM-D for the last non-missing postbaseline observations.

